Endogenous CS is characterised by chronic hypercortisolism, resulting in metabolic dysregulation and comorbidities. Manifestations may be overt or subtle depending on severity of hypercortisolism. Comorbidities include menstrual irregularities and hirsutism in women, dermatological problems with striae, bruising, atrophy, hyperpigmentation, and fungal infections, obesity with moon facies, enlarged supraclavicular fat pads, and dorsal fat pad, glucose intolerance and diabetes, sleep apnoea, cardiovascular disease, venous thromboembolic events, bone loss, neuropsychiatric disease, and potentially severe infections. Whereas untreated Cushing's syndrome had a 50% five-year mortality rate, treatment to control cortisol production should substantially mitigate the risk of death due to hypercortisolism (Nieman et al. 2015).

Endogenous CS is a rare disease. Estimates of regional incidence have been limited and vary by aetiology and possibly methodology. CD is the most common cause of endogenous CS, with an estimated incidence in Europe of up to 2.4 per million and in the US of up to 7.6 per million depending on the series (Etxabe and Vazquez 1994; Broder et al. 2015; Tabarin et al. 2022). Adrenal tumours represent ~20% of CS cases (but may be higher in some countries such as Japan (Tanaka et al. 2020) and Italy (Invitti et al. 1999). Ectopic ACTH secretion from neuroendocrine tumours represent 10-15% of known CS cases. Different diseases causing CS manifest at different ages, i.e., smoking-related non-small lung cancer increases after the age of 50 years, neuroendocrine (carcinoid) tumours

Final v2.0 26 of 63 18 April 2023

occur earlier in adulthood, and adrenal tumours have bimodal age peaks (1st decade and 40-50 years old), whereas the peak incidence for CD is in women 25-45 years old (Bertagna and Orth 1981; Luton et al. 1990). CD occurs approximately 3 times than in men, women have a 4-5 times greater incidence of adrenal tumour causing CS, and neuroendocrine tumours causing CS are similar in incidence between the sexes (Carpenter 1988; Nieman et al. 2015). Heterogeneity in the cause and populations affected by non-CS CS, support the need of a dedicated efficacy and safety study focusing on non-CD CS population. Patients with CS have increased mortality, which applies both to patients with pituitary-dependent CS and adrenal-dependent CS, as well as patients with ectopic CS who have the worst prognosis (Ragnarsson et al. 2019).

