# RECORDATI AG, Rare Diseases Branch LCI699-RECAG-NI-0596

Statistical Analysis Plan

objection letter (NOL) will be requested from the patient if still alive. If patient does not send the NOL back to the investigator, the investigator can document a tacit approval from the patient if there is no response after a month of the first shipment of the NOL and after 3 documented contact attempts. For a deceased patient since his/her past treatment with osilodrostat, access after the investigator has checked that this deceased patient did not leave any written document stating his/her refusal to participate in any scientific research.

Investigators will manually review and abstract clinical information from selected patients' medical records and will enter information into the electronic case report form (eCRF) from the date of initiating Osilodrostat through the follow-up period. All data are safeguarded using industry-best security practices to prevent unlawful disclosure and practices are compliant with Title 21 Part 11 policies of the Code of Federal Regulations. The HIMS software used for EDC purposes include password protection and encryption for all transmitted data. The platform will be approved by Recordati prior to study data abstraction or during site selection procedure.

The follow-up period will be variable, from the start of their osilodrostat onset period until the earlier of loss to follow-up, death, the end of the retrospective follow-up period or treatment discontinuation occurs. The patients with a potential follow-up of at least 12 weeks will be part of the primary analysis. The only patients excluded from the primary efficacy analyses will be the ones who started treatment with osilodrostat less than 12 weeks prior to the end of the abstraction period and are still treated with osilodrostat at the end of the abstraction period. These patients will be included only in the analyses of the secondary and exploratory endpoints including safety. The patients who discontinued treatment for any reason or were lost-to-follow up prior to 12 weeks will be considered non-responders for the primary endpoint. The end of study is defined as the last available assessment after treatment initiation for the last patient.

The timing of data collection is summarized in the Figure 1/Table 1.

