#### 5.2 General Presentation Considerations

All report outputs will be produced using SAS® version 9.4 or a later version in a secure and validated environment. All report outputs will be provided to the Sponsor in a single Microsoft Word document. Medical history, procedural/surgical history, and Adverse Events (AE) will be coded using the current version of the Medical Dictionary for Regulatory Activities (MedDRA). The frequency count and percentage of participants will be summarized according to the coded terms of system organ class (SOC) and preferred term. Participant-wise data listing will be provided.

Using the World Health Organization Drug Dictionary (WHO DD), prior and concomitant medications will be tabulated by drug classification, preferred drug name and study group.

Continuous data will be summarized in terms of the descriptive statistics, number of observations (n), mean and SE of mean or 95% CI of mean (as appropriate), SD, median and associated 95% CI of median (as appropriate), minimum, and maximum, unless otherwise stated.

Continuous data that are expected to be skewed and will be presented in terms of the maximum, upper quartile, median, lower quartile, minimum and number of observations. The mean, median will be reported to one more decimal place than the raw data recorded in the database. The SD will be reported to two more decimal places than the raw data recorded in the database. In general, the maximum number of decimal places reported shall be four for any summary statistic.

Project Document Version No.: 4.0; Document Effective Date: 30 October 2023

CONFIDENTIAL

Page 18 of 31

TP-GDO-WW-096-09 Effective Date: 22 Dec 21

Related to: SOP-GDO-WW-019

Categorical data will be summarized in terms of the number of participants providing data at the relevant time point (N), frequency counts and percentages.

Time to event endpoints will be summarized in terms of participants providing data, median and quartiles and represented graphically by Kaplan-Meier curves.

Percentages will be presented to one decimal place. Percentages will not be presented for zero counts. Percentages will be calculated using N as the denominator.

Changes from baseline in categorical data will be summarized using shift tables where appropriate.

Confidence intervals will be presented to one more decimal place than the raw data.

95% confidence intervals for proportions will be calculated using the exact (Clopper-Pearson) method, unless stated otherwise.

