#### 5.3.2 Analysis of the Primary Endpoint

The mean UFC for a participant at any particular visit is collected in the site. If mean UFC is not available at that visit, the mean UFC will be computed based on two or more individual 24hr UFC specimens at that visit. If there are only one individual 24hr UFC specimen available at that visit, then this one individual 24hr UFC specimen will be considered as mean UFC with the acknowledgement of clinical practice in France where one 24 hours UFC can inform on clinical decision.

The primary endpoint is the number and proportion of participants with mUFC ≤ ULN at 12 weeks will be summarized descriptively along with associated 95% CI. The participants who discontinued treatment prior to 12 weeks for any reason or were lost-to-follow up will be considered non-responders for the primary endpoint. The participants who started treatment with osilodrostat less than 12 weeks prior to the end of the abstraction period and are still treated with osilodrostat at the end of the abstraction period will be excluded from the analysis.

Project Document Version No.: 4.0; Document Effective Date: 30 October 2023

CONFIDENTIAL

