#### 5.3.3.10 Time to normalization

Time to normalization is the interval between start of osilodrostat administration and time of normalization of cortisol levels.

Project Document Version No.: 4.0; Document Effective Date: 30 October 2023

CONFIDENTIAL

RECORDATI AG, Rare Diseases Branch LCI699-RECAG-NI-0596

Statistical Analysis Plan

The participants not reaching the normalization will be censored at the date of the last available cortisol measure.

In the case of the composite analysis the baseline would be the closest measure to the start of osilodrostat among the different cortisol assessments (mUFC, salivary and serum) and the time of normalization is the first occurring among the cortisol measures. Censored dates will be the date of the last available cortisol measure. In case of multiple measures at a timepoint the the definition of composite normalization will be applied.

This will be reported for mUFC, salivary cortisol and morning serum cortisol as well as the combination of the 3 measures (any of the measures and reported as "Cortisol").

The number and proportion of events and censored values will be presented together with median time, (95% CI), quartiles, minimum and maximum and Kaplan-Meier curves will be produced for analysis.

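### Time to normalization (SAP 5.3.3.10) censors patients who die or stop osilodrostat before normalising, so the Kaplan-Meier curve and quartiles overstate normalisation and the median may be too short

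*SAP*

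**What the plan says.** SAP 5.3.3.10 measures the interval from the start of osilodrostat to normalisation, separately for mUFC, salivary cortisol, morning serum cortisol and the combination of the three. The censoring rule is: "The participants not reaching the normalization will be censored at the date of the last available cortisol measure". For the composite it repeats: "Censored dates will be the date of the last available cortisol measure". No reason for leaving is treated differently. The outputs are a crude count and a survival summary: "The number and proportion of events and censored values will be presented together with median time", its 95% CI and quartiles, and "Kaplan-Meier curves will be produced for analysis". The general rule in SAP 5.2 is the same: "Time to event endpoints will be summarized in terms of participants providing data, median and quartiles and represented graphically by Kaplan-Meier curves".

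SAP section 3 defines follow-up as running "until the earlier of loss to follow-up, death, the end of the retrospective follow-up period or treatment discontinuation occurs", and the footnotes to SAP Table 1 give the same four reasons for the end of data collection. Neither section names a competing-risk method. SAP 5.3.5 plans no formal sensitivity analysis; its additional populations apply to the primary endpoint only.

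**The concern.** Kaplan-Meier lets a censored patient stand for someone who will go on to normalise at the same rate as those still under follow-up. That is reasonable for a patient who reaches the end of the retrospective period. It is not reasonable for a patient who has died. A patient who has stopped osilodrostat can no longer normalise on it, and data collection has ended.

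SAP 5.3.3.10 does not mention death or discontinuation. Their censoring follows from reading it with the follow-up definition in SAP section 3 and the Table 1 footnotes. Censoring at the last cortisol value, which normally precedes the exit date, removes such patients from the risk set even earlier. One with no post-baseline value contributes nothing.

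At stake is the apparent speed and completeness of response. A reader of the curve, or of the median and quartiles taken from it, would see more and possibly faster normalisation than the cohort experienced, in a study meant to support an sNDA.

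**Working it through.** The documents give no expected median, event count or exit rate for this endpoint, so there is no plan figure to reproduce. The check compares one minus Kaplan-Meier (1−KM), with exits censored, against the cumulative incidence function (CIF), in which a patient who has died or stopped stays in the denominator as not normalised.

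**Inputs.** Protocol section 6 describes a phase II study in non-CD CS with nine patients: six complete responders at week 12, and two who discontinued at or before week 12 because of adverse events. I take F1 = 6/9 normalised and F2 = 2/9 out by week 12. Assumptions: constant hazards, and neither patient who stopped had normalised first.

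**Formulas.** Let λ be the weekly hazard of normalisation and μ that of death or discontinuation.
- λ + μ = −ln(1 − F1 − F2)/12, and λ = (λ + μ) × F1/(F1 + F2)
- 1−KM(t) = 1 − exp(−λt); median = ln 2/λ
- CIF(t) = [λ/(λ + μ)] × [1 − exp(−(λ + μ)t)]; median = −ln(1 − 0.5(λ + μ)/λ)/(λ + μ)

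**Anchor case.**
- λ + μ = ln 9/12 = 0.1831; λ = 0.75 × 0.1831 = 0.1373; μ = 0.0458
- 1−KM(12) = 1 − exp(−1.648) = 80.8%
- CIF(12) = 0.75 × (1 − 1/9) = 66.7%
- Medians: 0.6931/0.1373 = 5.05 weeks against ln 3/0.1831 = 6.00 weeks

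**Range (assumed shares, same formulas).**

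| Normalised by wk 12 | Died or stopped by wk 12 | 1−KM, wk 12 | CIF, wk 12 | Median, KM (wk) | Median, CIF (wk) |
|---|---|---|---|---|---|
| 40% | 5% | 41.2% | 40.0% | 15.65 | 16.59 |
| 40% | 30% | 49.7% | 40.0% | 12.09 | 20.73 |
| 50% | 20% | 57.7% | 50.0% | 9.67 | 12.00 |
| 66.7% | 5% | 69.1% | 66.7% | 7.09 | 7.34 |
| 66.7% | 22.2% | 80.8% | 66.7% | 5.05 | 6.00 |
| 66.7% | 30% | 90.4% | 66.7% | 3.55 | 4.55 |

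**Hand count without a hazard model.** Take nine patients: two normalise at each of weeks 4, 8 and 12 (assumed), one is followed to week 12 without normalising, and two stop. If the last value of the two who stop is at baseline, KM survival at week 12 is 5/7 × 3/5 × 1/3 = 1/7, so 1−KM = 85.7%. If it is at week 4, survival is 7/9 × 3/5 × 1/3, giving 84.4%. If it is at week 8, survival is 7/9 × 5/7 × 1/3, giving 81.5%. The observed share is 6/9 = 66.7% each time. If their last value is at week 12, there is no difference.

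**Simulation on the SAP visit grid.** N = 100, censoring at the last measure, administrative end uniform on 12 to 156 weeks (assumed), 300 runs per scenario. At the anchor rates, 1−KM against CIF was 80.6% against 60.3% at week 12 and 97.9% against 67.2% at week 36; the crude proportion of events was 66.8%. The week-12 CIF is below 66.7% because normalisation is seen only at a visit, and some patients leave before the next one. Over 15 scenarios (40%, 50% or 66.7% normalised; 5% to 30% out by week 12) the median was later with the CIF in 8, unchanged in 7 and earlier in none.

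**The case against.** The strongest defence is that censoring at discontinuation estimates what would have happened had patients stayed on treatment. That is a legitimate quantity, but the SAP does not state it. It also needs stopping to be unrelated to the chance of normalising, and it has no useful meaning for death. It can justify a supportive curve, not the only one.

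Several stronger readings are tempting, and the documents do not support them.
- *The rule contradicts the primary analysis.* SAP 5.3.2 says that those who "discontinued treatment prior to 12 weeks for any reason or were lost-to-follow up will be considered non-responders", but limits this to the primary endpoint, a proportion at a fixed week. It also fails patients lost to follow-up, whom a competing-risk analysis would properly censor. The two analyses treat early stoppers differently; that alone is not an error.
- *Competing exits are common and reflect poor control.* No rate is given for this cohort. Protocol section 6 refers to "patients with ectopic CS who have the worst prognosis", which concerns mortality, not leaving before normalisation. In the phase II study both discontinuations were for adverse events and nobody died. Pre-surgical users (SAP 3.5) who normalise before surgery count as events.
- *Every reported share is inflated.* The crude proportion of events in 5.3.3.10 is not. The SAP plans no table of Kaplan-Meier shares at fixed weeks.
- *The median is certainly shortened.* On the visit grid it often does not move.
- *The dates needed are all to hand.* SAP 5.9.5 acknowledges that end-of-treatment dates are often missing.

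The endpoint is also absent from the list in SAP 3.6.2 and from Protocol Table 1, and carries no hypothesis. That limits the severity.

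**Conclusion.** The point holds for the Kaplan-Meier curve and its quartiles, which overstate normalisation whenever patients die or stop before normalising and others normalise later. The median may be too short. The primary result, the by-visit proportions and the crude event count are unaffected.

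The direction does not depend on assumptions, because 1−KM cannot fall below the cumulative incidence when competing exits are censored. The size does. It is 14.1 points at week 12 (80.8 − 66.7) and 0.95 weeks in the median (6.00 − 5.05) at the phase II anchor, and 1.2 to 23.7 points and 0.25 to 8.64 weeks over the assumed range. The anchor rests on nine patients and constant hazards. If few patients leave before normalising, the effect is small. For a descriptive, supportive analysis, severity is modest, but the correction is worth making.

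**What to change.** Amend SAP 5.3.3.10 as follows.
- Make the Aalen-Johansen cumulative incidence of normalisation the main display, with death and permanent osilodrostat discontinuation before normalisation as competing events. Censor only at loss to follow-up or the end of the retrospective period.
- Date discontinuation with the existing approaches A and B of SAP 5.9.5 and show both. Let the reason for ending, not the presence of an imputed date, decide whether the exit is a competing event, because both approaches also give an end-of-treatment date to patients who simply reach the end of the retrospective period. Say how administrative endings are classed, and what is done where A leaves the date missing.
- State whether cortisol values recorded after a change to 0 mg count. SAP 3.3 allows that change to precede the end of study, and the present wording would use such values.
- Report the median as the time at which cumulative incidence reaches 50%, or as 'not reached'.
- Kaplan-Meier with discontinuation censored may stay as supportive, labelled as a 'had they stayed on treatment' quantity.

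The cost is SAP wording and standard software, with no new data collection. The drawbacks are less favourable figures and some dependence on imputed end-of-treatment dates.

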#### 5.3.3.11 Proportion of participants who experienced TEAE and AESI

A treatment-emergent adverse event (TEAE) is defined as an AE that begins or that worsens in severity after at least one dose of osilodrostat has been administered. The start date of adverse events will be compared with date of first dose of osilodrostat and the date of the earlier of loss to follow-up, death, the end of the retrospective follow-up period or treatment discontinuation occurs, whichever is earlier.

TEAE will be coded according to the latest Medical Dictionary for Regulatory Activities (MedDRA) terms and summarized by MedDRA System Organ Class (SOC) and Preferred Term.

Adverse Events of Special Interest (AESI) will be defined as following AEs:

- Adrenal hormone precursor accumulation-related AEs
- Hypocortisolism-related AEs
- Pituitary tumour enlargement-related AEs
- Arrhythmogenic potential and QT prolongation AEs

All AEs will be assessed according to incidence, grade, causality, outcome, action taken and seriousness. The details are provided in the safety analysis section 5.10.1 below.

